5.3. CRITERIA FOR SCHEDULE ADJUSTMENT/DOSE-MODIFICATION OR DISCONTINUATION OF THE IMP

5.3.1. Criteria for schedule adjustment/dose-modification

No schedule adjustment and/or dose modification is foreseen, except for discontinuation of IMP as detailed below.

5.3.2. Criteria for discontinuation of the IMP

The IMP will be discontinued in the case:

- QTcF is either > 500 msec or increases by > 60 msec from screening measurement on two consecutive ECG readings taken 1 hour apart;
- The patient develops any significant cardiovascular disease/abnormality;
- The patient develops renal (calculated eGFR < 60 mL/min) or hepatic (increased ALT/AST > 3 x ULN and increased total bilirubin > 3mg/dL [$>51.3 \mu\text{mol/L}$]) dysfunction as well as hypoalbuminemia (serum albumin <3 g/dL);

- Pregnancy occurs (subjects of child-bearing potential);
- The patient develops Diabetic Ketoacidosis (**DKA**) or hypoglycemic coma.

Occurrence of any condition that qualify the patient to treatment discontinuation will be specifically monitored through ECG readings and safety laboratory tests obtained at week 4 (visit 2b) and 11/12 (visit 3) during treatment. Pregnancy (urine dipstick) will be also tested at week 11/12 (visit 3).

In addition, the IMP will be immediately discontinued in the event of any other possibly drug related occurrences that the study physician believes might compromise patient's safety.

If the IMP administration is prematurely discontinued, the primary reason for discontinuation must be recorded in the eCRF. Patients who discontinue the treatment with the IMP will NOT be withdrawn from the study by default but will be asked to complete safety and efficacy observations as per the protocol, unless otherwise they withdraw their consent.

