2. SCHEDULE OF EVALUATION

The grid below summarizes the study schedule and the patient visits of the trial. For all measurements, the actual date and time of assessment, including date of sampling, will be recorded in the Source Document and/or eCRFs. Timeframe for each assessment is also shown in the grid below.

ACTIVITY	PRESCREENING* (Identify and reach out to potential participants and offer ICF)	Screening Visit 1 (Within week -2)	Treatment phase (week 1 to 26)			End of study Visit 4 (week 27/28)
			Randomization Visit 2 (Day 1)	Visit 2b (week 4)	Visit 3 (week 11/12)	
Presentation of trial and ICF	X	X				
Informed Consent Form (ICF) signed		X				
Medical history and pre-existing conditions		X				
Auto-antibodies evaluation¹		X				
Fasting C-peptide		X				
Measurement of body weight, height, waist, and waist/hip circumference		X	X		X	X
██████████ BMI assessment		X	X		X	X
Average (previous 3 days) Insulin requirement		X	X		X	X
HbA1c		X	X		X	X
CGM download for assessment of glycemic variability (previous 7 days)²			X		X	X
Vital signs		X	X		X	X
Serum Pregnancy Test (blood/urine)		X			X ³	
Safety laboratory tests (hematology, biochemistry)		X		X	X	X
CCI ██████████			████		████	X
ECG (QTcF)		X		X	X	X
eGFR		X			X	X
Randomization			X			
IMP dispensation.			X		X	
Patient Diary delivery/check			X		X	X
Treatment			X-----X			
Patient Phone call⁵			X-----X			
AE/SAE recording			X-----X			
Prior and Concomitant Medication			X-----X			

* Prescreening procedures can be performed during screening visit if applicable as per site practice

Legend:

1. To include new testing should past data not be available;

2. Secondary ;
3. Urine dipstick;

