2.4. PHARMACOKINETICS AND PRODUCT METABOLISM

The pharmacokinetics of DF2156Y was studied in rats and mice after single i.v. and oral administration and after multiple oral administrations in rats and dogs within the toxicity studies.

DF2156Y is almost completely absorbed after oral administration in rats with an absolute bioavailability higher than 90%. DF2156Y is slowly eliminated from plasma in all the three species tested ($t_{1/2}$ ranging from 25 hours to 30 hours). Gender differences in pharmacokinetic profile after oral administration (slightly lower exposure in females than in males) were observed in rats but not in dogs.

A metabolite of DF2156Y named DF2108Y (R enantiomer) was identified, using a non-chiral analytical method, in both rats and dogs. On the basis of the chiral analytical determination, the S enantiomer (DF2227Y) was noted in the plasma of both rats and dogs. The *in vivo* interconversion of DF2108Y into DF2227Y was about 90% in rats.

In male and female rats DF2227Y was the major and long-lasting circulating metabolite. After repeated daily oral administration of ladarixin, this metabolite showed an accumulation ratio ranging between 1.4 and 2.4. After the daily oral administration of ladarixin at 200 mg/kg for 6 weeks, the parent compound and the metabolites showed comparable exposure in Wistar and Sprague Dawley rats either at day 1 or after repeated administrations.

In humans, single oral doses of ladarixin (25 to 400 mg) provided quantifiable plasma concentration of DF2156Y within 1 hour, with peak concentration being reached between 1 and 3 hours. After single doses, DF 2156A was excreted mainly as unmodified in human urine. The presence of the two metabolites found in animal species (DF 2108Y and DF 2227Y) was confirmed in humans. Dose proportionality over the entire dose range investigated was observed as well as $t_{1/2}$ (11-19 h) remained constant across the range of doses evaluated. Renal clearance accounted for approximately 60-80% of the total clearance of ladarixin. The dose proportionality for the main PK parameters was also seen for the two metabolites (DF 2108Y and DF 2227Y).

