12. history of ≥ 1 Diabetic Ketoacidosis (**DKA**) event in the past 6 months;
13. hypoalbuminemia defined as serum albumin < 3 g/dL;
14. hepatic dysfunction defined by increased ALT/AST > 3 x upper limit of normal (**ULN**) **and** increased total bilirubin > 3 mg/dL [> 51.3 μ mol/L];
15. moderate to severe renal impairment calculated by estimated Glomerular Filtration Rate (**eGFR**) < 60 mL/min/1.73 m² as determined using Chronic Kidney Disease Epidemiology Collaboration (**CKD-EPI**) creatinine equation;
16. past (within 1 month prior to screening) or current administration of any immunosuppressive medications (including oral or systemically injected steroids) and use of any investigational agents, including any agents that impact the immune response;
17. a condition already known which interferes with the ability to accurately determine glycated HbA1c. Examples include: genetic variants (e.g. HbS trait, HbC trait), elevated fetal hemoglobin (HbF) and chemically modified derivatives of hemoglobin (e.g. carbamylated Hb in patients with renal failure); any condition that shortens erythrocyte survival or decreases mean erythrocyte age (e.g., recovery from acute blood loss, hemolytic anemia); iron deficiency anemia, iron replacement therapy;
18. significant systemic infection during the 4 weeks before the first dose of study drug (e.g., infection requiring hospitalization, major surgery, or i.v. antibiotics to resolve; other infections, e.g., bronchitis, sinusitis, localized cellulitis, candidiasis, or urinary tract infections, must be assessed on a case-by-case basis by the investigator regarding whether they are serious enough to warrant exclusion).

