Visit 2b: (Week 4): An ECG will be performed and then the subject will undergo blood sampling for assessment of safety laboratory testing.

Visit 3: (Week 11/12): Patient Kits (cycle 1 to 3) and the Diary will be returned to and checked by the study staff to verify inventory and treatment compliance. Medication use will be also ascertained. Vital signs will be measured followed by an ECG, and then the subject will undergo blood sampling for assessment of HbA1c and safety laboratory testing and exploratory outcome measures CCI [REDACTED]; average (previous 3 days) daily insulin requirements (IU/kg/day) will be recorded, body weight, height, waist and waist/hip circumference will be measured and [REDACTED] CGM data will be downloaded for measurement of glycemic variability in the previous 7 days. After IMP discontinuation criteria have been checked, Patient Kits (cycle 4 to 7) will be dispensed and the subject will be discharged from this visit.

Visit 4; End of Study (Week 27/28): The study subject will come to the clinic for final assessment of vital signs, ECG, average (previous 3 days) daily insulin requirements (IU/kg/day), body weight, height, waist and waist/hip circumference and for [REDACTED]. Subjects will undergo blood sampling for assessment of HbA1c, safety laboratory testing, eGFR and exploratory outcome measures CCI [REDACTED] CGM data will be downloaded for measurement of glycemic variability in the previous 7 days.

At the end of the visit, upon the study physician's order, the subject will be formally discharged from the study.

REGULARLY-SCHEDULED PHONE CALLS: In-trial, the sub-investigator/study coordinator will proactively reach out to study subjects, at least every 30-45 days, for the entire study period from the time

of randomization visit onwards, to ensure compliance with treatment and importantly, ongoing identification of any AEs. It is the responsibility of the PI to adjust the frequency of such contacts, according to patient responsiveness and compliance with treatment.

Unscheduled visits

In addition to the scheduled visits, it is possible that subjects may need to complete an unscheduled visit if they experience an event that the PI or the Principal Physician believes to warrant follow-up. The unscheduled visit might include appropriate actions, such full physical examination and blood sample collection (less than 30 mL) that the PI or the Principal Physician feels is required, based upon the event.

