7.2. SAFETY ENDPOINTS

- Vital signs (blood pressure and heart rate) [Timeframe: screening, week 11/12 (visit 3), 27/28 (visit 4)]
- Laboratory tests [haematology (total WBC, neutrophils/lymphocytes/monocytes/basophils/eosinophils (% and absolute number), total RBC, MCV, hematocrit, platelet count) and clinical chemistry (sodium, potassium, serum creatinine, serum albumin, total bilirubin, ALT, AST)] [Timeframe: screening, week 11/12 (visit 3) and 27/28 (visit 4)]
- Incidence of Treatment Emergent Adverse Events (TEAEs), Adverse Drug Reaction (ADR) and Treatment Emergent Serious Adverse Events (TESAEs) [Timeframe: from the beginning of IMP administration up to the end of study participation].

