14.4.2. Calculation of eGFR

Renal function will be evaluated by estimated Glomerular Filtration Rate (eGFR), calculated by the following formula²⁰⁶:

Calculate eGFR using the CKD-EPI formula

Gender?	
Male	
Female	
Race?	
Not African-American	
African-American	
Age?	Years
Unanswered	
Creatinine?	mg/dL
Unanswered	

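### Protocol 5.3.2 relies on week 4 to detect every stopping condition, but eGFR, which defines the renal one, is not scheduled at week 4, and its unit differs from exclusion 15

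*Protocol*

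**What the plan says.** **Stopping rule.** Protocol 5.3.2 discontinues the study drug when "The patient develops renal (calculated eGFR < 60 mL/min) or hepatic" dysfunction develops, among other conditions. It adds that any condition qualifying for discontinuation "will be specifically monitored through ECG readings and safety laboratory tests obtained at week 4 (visit 2b) and 11/12 (visit 3) during treatment".

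**Entry rule.** Exclusion 15 in section 4.2, repeated in the synopsis, excludes eGFR "< 60 mL/min/1.73 m² as determined using Chronic Kidney Disease Epidemiology Collaboration" creatinine equation.

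**Calculation.** Section 14.4.2 gives one method for the study: "Calculate eGFR using the CKD-EPI formula". The fields are gender, race, age and creatinine.

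**Schedule.** In section 2, the row "Safety laboratory tests (hematology, biochemistry") is marked at screening and visits 2b, 3 and 4. eGFR has its own row, marked at screening and visits 3 and 4 only. For visit 2b, section 6.1.2 says: "An ECG will be performed and then the subject will undergo blood sampling for assessment of safety laboratory testing". For visit 4 the same section names eGFR in addition to safety laboratory testing.

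**Panel.** Section 7.2 lists "clinical chemistry (sodium, potassium, serum creatinine, serum albumin, total bilirubin, ALT, AST").

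**Dispensing.** Under section 6.1.2, kits for cycles 1 to 3 are handed out at visit 2. Kits for cycles 4 to 7 follow at visit 3, once the stopping criteria have been checked. The visit 2b text contains no such check.

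**The concern.** A stopping rule works only if the quantity it names is obtained when the rule is meant to be applied. The renal rule is written in eGFR, not in creatinine. Section 5.3.2 counts on week 4 as one of two on-treatment checks, but the documents that a site works from, the grid and the visit text, do not ask for eGFR then. Because the protocol lists eGFR apart from the safety laboratory tests, a site has reason to think that it is not due at visit 2b.

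The renal criterion matters for this drug. Section 2.4 reports: "Renal clearance accounted for approximately 60-80% of the total clearance of ladarixin". Reduced renal function would therefore be expected to raise exposure. Section 2.6.2.1 also points to sections 5.3.2 and 6 when it says that risk is limited by monitoring at planned intervals, and for this criterion those two sections do not line up.

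The unit is a second, smaller matter. Entry and stopping use the same number, 60, with different unit labels, and 5.3.2 names no equation. A threshold that ends treatment should have one reading.

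**Working it through.** The plan gives no figure to reproduce here. The check is a comparison of sections, then the timing, then the size of the unit question.

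**1. What each visit asks for** (sections 2 and 6.1.2)

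| Visit | Safety laboratory tests in grid | eGFR in grid | Check of stopping criteria in visit text |
|---|---|---|---|
| 1, screening | yes | yes | not applicable |
| 2, Day 1 | no | no | not applicable |
| 2b, week 4 | yes | **no** | **no** |
| 3, week 11/12 | yes | yes | yes |
| 4, week 27/28 | yes | yes | treatment already finished |

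Section 5.3.2 relies on the rows for visits 2b and 3. For the renal criterion, only visit 3 has all that is needed.

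**2. Timing**

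- Treatment is 7 cycles of 14 days on with 14 days off between them: 7 × 14 + 6 × 14 = 182 days = 26 weeks, as the protocol states.
- Cycle 1 is dosed in weeks 1-2, cycle 2 in weeks 5-6 and cycle 3 in weeks 9-10. Visit 2b (week 4) and visit 3 (week 11/12) fall in off periods, as section 6.1.2 says.
- From week 4 to week 11 or 12 is 11 − 4 = 7 weeks or 12 − 4 = 8 weeks.
- Cycles 2 and 3 lie in that interval: 2 × 14 = 28 dosing days.
- If no eGFR is calculated at week 4, the first scheduled on-treatment value comes after 3 of 7 cycles, that is, 3 × 14 = 42 of 7 × 14 = 98 dosing days.

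**3. Whether the data exist at week 4**

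Of the four inputs in section 14.4.2, gender, race and age are already known and creatinine is in the panel of section 7.2. The assumption is that the week-4 biochemistry is this same panel. The grid uses one row for all visits and gives no other panel. On that assumption eGFR can be calculated at week 4 without another sample.

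**4. The unit**

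If mL/min were taken literally as a value not indexed to body surface area (BSA), then eGFR in mL/min = eGFR in mL/min/1.73 m² × BSA/1.73. A threshold of 60 mL/min would then equal 60 × 1.73/BSA on the indexed scale. BSA by Mosteller = √(height in cm × weight in kg / 3600), with weight = BMI × (height in m)². The BMI limits of 24 and 33 are the protocol's; the heights are assumed.

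| Height, BMI | Weight (kg) | BSA (m²) | 60 mL/min on the indexed scale |
|---|---|---|---|
| 160 cm, 24 | 61.4 | 1.65 | 62.8 |
| 170 cm, 24 | 69.4 | 1.81 | 57.4 |
| 170 cm, 33 | 95.4 | 2.12 | 48.9 |
| 190 cm, 33 | 119.1 | 2.51 | 41.4 |

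Over assumed heights of 150 to 200 cm and BMI 24 to 33 the range is about 38 to 69. The Du Bois formula gives results within about 2 units.

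If eGFR is calculated as section 14.4.2 describes, no height, weight or surface area enters. The stopping threshold then equals the entry threshold at every body size, and the difference is zero.

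**The case against.** **On week 4.** Section 5.3.2 does not say that eGFR is obtained at week 4. It says that stopping conditions are monitored through ECG and safety laboratory tests, and those are scheduled at visit 2b. Creatinine is in the panel, the criterion is described as calculated, and a careful investigator would calculate it. Silence in the visit 2b text proves little by itself, because the visit 1 and visit 3 texts also leave out eGFR although the grid marks it there. Section 5.3.2 also lets the study physician stop the drug for any possibly drug-related event that threatens safety.

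Most of this stands, and it limits the point to a missing instruction. It does not remove the point. At visits 1 and 3 the grid supplies what the text omits; at visit 2b neither does. A general power to stop does not replace a defined threshold.

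**On the unit.** A reader might infer that the stopping rule fires late, or never, in a large patient, that a small eligible patient meets it on Day 1, or that two sites would decide differently on the same creatinine. The documents do not support this. All three need a conversion to mL/min that no section describes, and section 14.4.2 has no body-size input. Even on the literal reading the threshold only moves, down in larger patients and up in smaller ones; it does not disappear.

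**On section 7.2.** A reader might also count the absence of week 4 from its laboratory timeframe as an error. That timeframe describes an endpoint, not the collection schedule, and section 9.4.2.3 summarises laboratory tests at each available visit. It is not part of this point.

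**Conclusion.** The point holds as an inconsistency between sections that bears on a safety rule. Section 5.3.2 promises week-4 monitoring of every stopping condition, and the schedule and visit 2b text do not call for the quantity that defines the renal one. A site working from the grid may leave the renal criterion unapplied from week 4 to week 11/12, about 7 to 8 weeks and 28 dosing days, with those capsules already in the patient's hands. This assumes that the site calculates eGFR only where the grid marks it. If the site calculates it from the week-4 creatinine anyway, there is no gap.

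The unit difference is real but probably a labelling slip, with no effect if sites use the calculation in section 14.4.2. It deserves correction because a stopping threshold should not be open to two readings. Nothing here says which threshold is clinically right.

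**What to change.** - Reconcile the eGFR row of the schedule and the visit 2b text in section 6.1.2 and the synopsis with the monitoring sentence in 5.3.2, so that the stated week-4 monitoring of the renal criterion can be carried out from the creatinine already drawn. The reconciled text should also make clear whether the stopping criteria are to be checked at visit 2b, as they are at visit 3.
- Reconcile the unit in 5.3.2 with exclusion 15 and section 14.4.2. The sponsor decides which quantity and threshold are intended.

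The cost is wording, a grid entry and at most one calculated field in the eCRF. No extra sample or visit is needed.

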In studies with up to 1 week administration in dogs by oral route, the dose of ladarixin had to be reduced from 500 to 150 mg/kg, due to poor tolerability and severe clinical signs, namely tremor, vomiting, uncoordinated movements. No macro or microscopic findings were present; organ weights were not affected. In the 4-week oral toxicity study in dogs, ladarixin was administered up to the dose of 120 mg/kg. No mortality occurred. Vomiting was seen at 120 mg/kg. An increase in the absolute and corrected-for-heart rate QT interval was observed at the doses of 60 and 120 mg/kg. Inflammatory changes were seen in the duodenum of two males treated with 120 mg/kg. After 2 weeks all values returned to normal. It was concluded that the no observed-effect-level (NOEL) is 30 mg/kg/day.

In the 3-month study, the initial dose levels were 30, 60 and 120 mg/kg/day. However, due to test item-related moribundity of one high dose male and changes in body weight and food intake of a few other animals in the group, the highest dose level was lowered from 120 to 80 mg/kg/day from Day 24 onward. At 120/80 mg/kg/day, one male and one female showed weight loss (up to -7%) and lower food intake during the first weeks of treatment and the clinical condition was reduced in Week 4. Food supplements were provided, which resulted in an improved clinical condition and normal body weight (gain) of these animals during the remainder of the treatment period after reduction of the dose level from 120 to 80 mg/kg/day. Prolongation of the QT and/or corrected QT intervals was observed in males and females treated at 120/80 mg/kg/day in Weeks 4, 8 and/or 13, generally more pronounced in females. In addition, higher heart rates were noted for males and (individual) females treated at 120/80 mg/kg/day in Weeks 4, 8 and/or 13. At the end of the Recovery period, only one male and one female at 120/80 mg/kg/day were still on study, and all electrocardiography parameters were returned to the normal limits. For one female at 60 mg/kg/day, mixed cell inflammation of the brain parenchyma and meninges, with neuronal necrosis and gliosis was recorded at moderate degree. There were no correlating clinical signs or necropsy alterations noted for this animal.

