In the 9-month study, dogs were treated orally with DF2156A at doses of 30, 60 and 100 mg/kg. No mortality occurred during the study period. The test item was clinically well tolerated up to the high dose of 100 mg/kg/day, as all animals were in a good general condition until the end of study. ECG recordings in Weeks 13, 26 and 38 revealed a dose-related increase in (corrected) QT intervals in both males and females at 60 and 100 mg/kg/day at 2 to 4 hours after dosing, most prominently in Week 38. In addition, heart rates were increased in 100 mg/kg/day treated males and females at 2 and/or 4 hours post-dose in Weeks 13, 26 and/or 38 (females were more affected than males). The QT prolongation and increased heart rates in females at 100 mg/kg/day were considered to be adverse, based on the maximum increase in QTcF interval of 25.5 msec in Week 38 on a group mean basis, and based on the magnitude of change for heart rate. The No Observed Adverse Effect Level (NOAEL) for females was considered to be 60 mg/kg/day after 9 months of dosing. In males, the NOAEL was concluded to be at least 100 mg/kg/day.

In conclusion, based on the toxicology testing performed through in vivo studies, the dose of 150 mg/kg appears to represent the NOAEL in rats for general toxicity while in dog, in the 9-month oral toxicity study, the NOAEL was established at 60 mg/kg (taking into consideration the lowest in this study). In rats, 150 mg/kg is the NOAEL for developmental toxicity while in rabbits it was 100 mg/kg.

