6.1.2. Visit schedule and events/procedures

All subjects will follow the study procedures outlined below (see also grid in [Section 2](#) above).

Every effort should be made to adhere to the visit schedule. Visits should be scheduled at the designated time-point. If unavoidable, an unscheduled visit may be performed, but the schedule for subsequent visits must be maintained so that the total duration of the study period per patient is as close as possible to 30 weeks. If a visit is scheduled at a time other than the protocol designated time, careful consideration must be given to the amount of study medication the subject has available.

Patients should be counseled to fast (no food or drink except water and non-study medications as prescribed) for at least 8 hours prior to all study visits where blood will be collected.

Each patient will be involved in the study for a screening visit, a randomization visit, the treatment period of 26 weeks (14 days on /14 days off) with 3 follow-up visits to the clinical research site scheduled up to week 28 after the 1st IMP dose.

Visit schedule and events/procedures are detailed in the sections below. Visits 2b and 3 are scheduled during the 14 days off treatment, while visit 4 is set in the 2 weeks after treatment completion (last IMP dose in cycle 7).

CCI

Visit 1: Screening: The study physician or designee will present to/discuss with the study subject the clinical trial and answer all questions. If the patient is able and willing to participate, after the informed consent has been obtained, study staff will:

- assess past medical history to confirm T1D (e.g. results of past auto-antibody testing),
- determine daily insulin requirement (U/kg/day - expressed as the average of the last 3 days) and its stability,
- measure body weight, height, waist and waist/hip circumference,
- calculate [REDACTED] BMI,
- record the use of concomitant medication,
- establishing the presence of IR as described (inclusion criteria, bullet 8)¹⁻³.

Screening evaluation also include blood sampling for the assessment of:

- HbA1c,
- fasting C-peptide,
- standard safety laboratory tests,

- pregnancy in subjects with reproductive potential; post-menopausal women, defined as no menses for 12 months without an alternative medical cause, will not undergo pregnancy testing.
- T1D auto-antibody (excluding IAA) should past data not be available.

Vital signs (blood pressure and heart rate) will be measured and an ECG performed.

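### The QTcF stopping rule relies on ECGs at visits 2b and 3, both in off-treatment periods: visit 2b would miss an acute, reversible QT effect, and visit 3 would catch one only if held in the first few days

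*Protocol*

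**What the plan says.** Protocol section 5.3.2 requires the study drug to be stopped if QTcF is above 500 msec, or more than 60 msec above the screening value, "on two consecutive ECG readings taken 1 hour apart". It states that conditions qualifying for discontinuation will be "specifically monitored through ECG readings and safety laboratory tests obtained at week 4 (visit 2b) and 11/12 (visit 3) during treatment".

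Section 6.1.2 fixes the timing of those visits: "Visits 2b and 3 are scheduled during the 14 days off treatment, while visit 4 is set in the 2 weeks after treatment completion". The grid in section 2 lists ECGs at screening and at visits 2b, 3 and 4 only. There is none at visit 2, where the first dose is taken on site.

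The visit 3 check also controls further supply: "After IMP discontinuation criteria have been checked, Patient Kits (cycle 4 to 7) will be dispensed".

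Section 2.5.3 names QT prolongation as a potential human concern arising from the animal work. Section 2.6.2.1 counts ECG readings at planned intervals among the measures that limit risk, and refers to section 5.3.2.

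**The concern.** A stopping rule can act only on what the scheduled measurement can see. The protocol's own data describe a QT effect tied to dosing and reversible off drug. In the 9-month dog study (section 2.3) the increase was reported "at 60 and 100 mg/kg/day at 2 to 4 hours after dosing, most prominently in Week 38". After the 4-week dog study, "After 2 weeks all values returned to normal". At the end of recovery in the 3-month study, "all electrocardiography parameters were returned to the normal limits". In humans the drug is absorbed quickly, "with peak concentration being reached between 1 and 3 hours" (section 2.4).

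If a patient had a QTcF rise of this kind, ECGs taken only in off periods would tend to look normal. The patient would then be cleared to continue. The protocol would be offering a safeguard for QTcF that its schedule largely does not deliver.

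**Working it through.** **Inputs.** Seven cycles of 14 days on and 14 days off; evening dose ideally between 18:30 and 23:30 (section 5.2). Human parent half-life 11-19 h after single doses and 11-18 h after multiple doses; steady state around days 5-6 (section 2.4). Visit 2b in week 4, visit 3 in week 11/12, visit 4 in week 27/28 (section 2). Assumptions: day 1 is the first dose, visits are at 08:00, and decline after the last dose is single-exponential.

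**Calendar.** Cycle k is dosed on days 28(k-1)+1 to 28(k-1)+14. The total is 7 × 14 + 6 × 14 = 182 days = 26 weeks, which reproduces the stated duration. Dosing days: 7 × 14 = 98. Week 4 is days 22-28, with the last dose on day 14. Weeks 11-12 are days 71-84, with the last dose on day 70. Weeks 27-28 are days 183-196, with the last dose on day 182. None of these visit days is a dosing day.

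**Visit 2b.** Fraction left = 0.5^(hours / half-life).
- Shortest gap: day 14 at 23:30 to day 22 at 08:00 = 8 × 24 − 15.5 = 176.5 h.
- Longest gap: day 14 at 18:30 to day 28 at 08:00 = 14 × 24 − 10.5 = 325.5 h.
- Half-lives at the shortest gap: 176.5/19 = 9.3; 176.5/18 = 9.8; 176.5/11 = 16.0.
- Parent drug left at the shortest gap: 0.5^(176.5/19) = 0.16%; 0.5^(176.5/18) = 0.11%.
- A 09:00 visit gives 177.5 h and 0.15% at 19 h, so the assumed clock time hardly matters.

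**Visit 3**, at an 18 h half-life:

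| Day | Last dose 23:30: hours, % left | Last dose 18:30: hours, % left |
|---|---|---|
| 71 | 8.5 h, 72% | 13.5 h, 60% |
| 72 | 32.5 h, 29% | 37.5 h, 24% |
| 73 | 56.5 h, 11% | 61.5 h, 9.4% |
| 74 | 80.5 h, 4.5% | 85.5 h, 3.7% |

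More than 10% remains while hours < half-life × log2(10), that is below 36.5 h at 11 h, 59.8 h at 18 h and 63.1 h at 19 h. This covers 1-2, 2-3 and 3 days respectively, so 1-3 of the 14 permitted days. The shortest gap is 8.5 h, so no permitted time falls 2-4 h after a dose. Visit 4 has the same gaps but comes after the last dose and cannot stop anything.

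**Metabolites.** Human half-lives are not given. For more than 10% to remain at visit 2b on its first day, a metabolite half-life would have to exceed 176.5/log2(10) = 53 h.

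**The case against.** The strongest reply is that the risk looks small. Phase I included repeated dosing at up to 400 mg twice daily for up to 6 days, about as long as steady state takes to reach. Core-laboratory review of QTcF changes and of the concentration-effect relationship found no clinically significant effect on repolarization (section 2.5.3). The largest group-mean QTcF rise in the 9-month dog study was 25.5 msec, at 100 mg/kg/day in females, well below the 60 msec trigger, although a group mean says little about individuals. The normal 3-month recovery ECGs come from one male and one female. The protocol does not say whether dog ECGs were also read later than 4 h, so it is not shown that an effect would have gone by 8.5 h. All of this stands. It limits the weight of the point but does not give the rule an on-drug ECG.

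Other safeguards exist: physician judgement (5.3.2), unscheduled visits and calls (6.1.2), questions at each visit (8.2) and DMC review (12.5). They respond to events or to data already collected and do not screen for silent QTcF prolongation. Redacted text follows the timing sentence in 6.1.2 and may hold a rationale, but the visible grid has no on-drug ECG.

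Four stronger readings may tempt a reader and are not supported:
- **That the rule can never trigger.** A visit 3 ECG on the first permitted day may still find most of the parent drug present.
- **That the effect would grow over seven cycles because the dog effect was greatest in week 38.** The dogs were treated for 9 months with no off periods described. Here parent drug is almost gone before each new cycle.
- **That all the stopping criteria fail.** Off-drug laboratory tests can still show persisting liver, kidney or albumin changes.
- **That sections 5.3.2 and 6.1.2 contradict each other outright.** In 5.3.2 the words on treatment can be read as the 26-week treatment phase. The problem is the timing of the ECG.

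**Conclusion.** The point holds for QTcF as a weakness in monitoring sensitivity. No ECG is scheduled on any of 98 dosing days. Visit 2b cannot be expected to show an acute, reversible effect, with at most about 0.16% of parent drug left. Visit 3 has some sensitivity on its first one to three days and little after that, and it never samples the 2-4 h window. The protocol does not show that ladarixin prolongs QT in patients, and this point does not claim it.

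The conclusion rests on the parent half-life of 11-19 h, the dosing times in section 5.2, a morning visit, and an effect that follows drug exposure as the dog data suggest. An effect driven by a long-lived metabolite would change it; the protocol gives no human metabolite half-life with which to judge that. The change is worth making because it is cheap, and because section 2.6.2.1 relies on these ECGs.

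**What to change.** Move the existing visit 2b from week 4 to days 8-14 of cycle 1, when the drug is at steady state. At that visit take the fasting bloods first, give the morning dose on site, and record the ECG about 2 h later (allowed range 1-4 h). At 2-3 h the human peak and the dog window overlap. If a criterion is met, take the repeat 1 h later that 5.3.2 already requires; after a 2 h reading this falls at 3 h. Breakfast can follow the 2 h ECG, since section 5.2 already keeps doses at least 2 h from breakfast, and CGM covers the wait.

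Amend the synopsis, the section 2 grid and section 6.1.2 to match. In 5.3.2 state that the visit 2b ECG is on drug and the visit 3 ECG is off drug.

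Cost: no added visit or procedure. Visit 2b is about 2 h longer, or 3 h with a repeat ECG, and the fast lasts longer in insulin-treated patients. The off-drug laboratory check between cycles 1 and 2 is lost. It becomes an on-drug check 8 to 20 days earlier (22 − 14 to 28 − 8), and the next laboratory tests are at visit 3. A few more patients may stop the study drug; under 5.3.2 they stay in follow-up. The change gives each patient one on-drug ECG early in treatment and adds none in cycles 4-7.
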